### **3.2 Dose Rationale**

A total of three dosing cohorts (Cohorts 1-3) are planned. The planned doses of ciraparantag or placebo (administered as a volume equivalent of ciraparantag) have been evaluated as single and repeat IV doses from 5 mg ciraparantag acetate (3 mg ciraparantag) up to 600 mg ciraparantag acetate (360 mg ciraparantag) in previous protocols (PER977-01-001, PER977-01-002, PER977-01-003, and PER977-02-001). All doses of study drug will be administered by IV injection over a minimum of 10 minutes.

### **3.3 Study Duration and Dates**

Expectation of the total duration of the study is approximately 3 months. Individual subject participation is approximately 51 days inclusive of screening and follow-up. Subjects enrolled will spend up to 5 nights admitted to an in-patient facility.

## 4 STUDY POPULATION

### 4.1 Screening and Enrollment

The Investigator will maintain a confidential screening log of all potential study candidates that includes limited information of the subjects (age, sex), date and outcome of screening process (e.g., enrolled in the study, reason for ineligibility, refused to participate).

The Investigator will be expected to maintain an Enrollment Log of all subjects enrolled in the study indicating their assigned study number.

The Investigator will maintain a confidential subject identification code list. This confidential list of names of all subjects allocated to study numbers upon enrolling in the study, allows the Investigator to reveal the identity of any subject when necessary.

Each subject will sign an Informed Consent Form (ICF) prior to any study assessments.

Subjects should conform to the inclusion/exclusion criteria for the duration of the study. If a subject violates an inclusion or exclusion criterion at any point during the study, he/she may be removed from the study and replaced.

### 4.2 Study Population

The study population will consist of healthy male and female adults, age 50-75 years (inclusive).

No formal sample size calculations were performed for this study; sixteen (16) subjects enrolled in each cohort (3:1; active:placebo) is considered an adequate number of subjects to achieve the objectives of the study.

Estimated number of subjects screened:	120
Planned number of subjects randomized/dosed:	48
Planned number of evaluable subjects:	48

### 4.3 Inclusion Criteria

Each patient must meet the following criteria to be enrolled in this study.

1. Adults age 50 to 75 years, inclusive
2. Laboratory tests (chemistry, hematology and coagulation assessments) and urinalysis performed during screening up to 36 days prior to administration of study treatment deemed not clinically significant by the principal investigator.

3. No clinically significant findings on 12-lead electrocardiogram (ECG) performed during screening
4. Body mass index (BMI) 18 to  $\leq$  32 kg/m^2, inclusive
5. Male subjects agree to use appropriate contraception (i.e., latex condom with spermicide) in addition to their partner using an acceptable form of contraception (e.g., diaphragm, cervical cap, intrauterine device, hormonal contraceptives, surgical sterilization or post-menopausal), when engaging in sexual activity during the course of the study. Moreover, male subjects should not donate sperm or attempt to impregnate a partner during the course of the study and for a period of 12 weeks following discharge from the study.
6. Female subjects must have negative pregnancy tests at screening and check-in AND: be surgically sterile at least 6 months prior to the first dose (with documentation of hysterectomy, bilateral oophorectomy, bilateral salpingectomy, bilateral tubal ligation/tubal occlusion); OR post-menopausal (no menstruation for a minimum of 12 months and confirmed by follicle stimulating hormone [FSH] of  $\geq$  40 mIU/ml and serum estradiol  $<$  30 pg/ml); OR, if of child-bearing potential, must be using an acceptable method of contraception such as an IUD, implant or contraceptive injection, or **two** forms of the following (e.g., diaphragm, cervical cap, patch or vaginal hormonal contraceptive, condom, spermicide, or sponge) for the last three months. All females must agree to continue to use their method of birth control for the duration of the study and for a minimum of one complete menstrual cycle following discharge from the study
7. Subjects who have participated in a prior study of ciraparantag must have been discharged from the study a minimum of 1 months prior to the planned treatment.
8. Subjects must understand and agree to comply with the requirements of the study and they must be willing to sign the informed consent form indicating voluntary consent to participate in the study prior to initiation of screening or study-related activities

#### **4.4 Exclusion Criteria**

Patients who meet any of the following criteria will be excluded from the study.

1. History or current evidence of clinically significant cardiac, hepatic, renal, pulmonary, endocrine, neurologic, infectious, gastrointestinal (including gallbladder disease or surgery), hematologic, or oncologic disease as determined by screening history, physical examination, laboratory test results or 12-lead ECG assessment. History or current evidence of liver function tests greater than 50% of the upper limit of normal (ULN) or renal function tests (serum creatinine) greater than 1.5 mg/dl and based on PI discretion. History or current evidence of QTc (QTcF) greater than normal (450 msec for males or 470 msec for females).
2. History of unexplained syncope

3. History of major bleeding, trauma, or surgical procedure of any type based on PI discretion
4. Vaginal delivery within six months prior to screening
5. History of peptic ulcer, gastrointestinal bleeding (including hematemesis, melena, rectal bleeding) within one year prior to screening
6. Long standing history of bleeding episodes such as epistaxis, bruising or gingival bleeding or if not long standing, within 1 month prior to screening
7. Personal or family history of clotting disorder or abnormality, excessive bleeding, joint hematoma, thrombovascular disease or any hematologic disorder involving platelets or clotting abnormalities or any condition requiring treatment with transfusions, or history of thrombocytopenia
8. Females with a history of dysfunctional uterine bleeding who have not undergone hysterectomy, including history of menorrhagia (heavy menstrual bleeding), menometrorrhagia or polymenorrhea
9. Smokers or use of tobacco and/or nicotine containing products within 3 months prior to dosing as determined by the subject's verbal history
10. Pregnant or breast-feeding
11. Males with a history of hormone therapy within 3 months prior to screening
12. Administration of any blood product or anticoagulant within 3 months prior to study entry or any non-steroidal anti-inflammatory drug or cyclooxygenase inhibitor within 2 weeks prior to dosing
13. Taking any type of chronic medication (including vitamin, nutritional and herbal supplements) for more than 14 consecutive days within the 4 weeks prior to study entry (use of hormonal contraceptives is acceptable except for oral contraceptives)
14. Positive serologic test for human immunodeficiency virus (HIV), Hepatitis C virus antibody (HCV-Ab), or Hepatitis B surface antigen (HBsAg)
15. Donation of blood or blood products within 56 days prior to screening
16. Participation in any study with an investigational compound or device within 30 days prior to signing informed consent
17. Active drug or alcohol dependence within the prior 12 months or any condition that, in the opinion of the Investigator, would interfere with adherence to study protocol
18. Allergic to apixaban

## 5 STUDY TREATMENT(S)

### 5.1 Description of Treatment(s)

The following dosage forms will be provided for this study:

- Ciraparantag for IV injection
- Placebo for IV injection
- Apixaban 5 mg tablets (commercial formulation Eliquis®, Pfizer/BMS) for oral administration

All doses of study drug (ciraparantag or placebo) will be administered by IV injection (over a minimum of 10 minutes) e.g. 60 mg ciraparantag (10 ml) will be administered at a rate of approximately 1 mL/min and 360 mg (60 ml) will be administered at a rate of approximately 6 mL/min into an indwelling catheter that is not attached to an IV solution and will not result in dilution of the study drug. The indwelling catheter will be flushed with 5.0 mL of sterile 0.9% Sodium Chloride Injection, USP before and after administration of study drug. All doses of study drug will be administered in a single-blinded-fashion.

### 5.2 Treatments Administered

#### 5.2.1 Ciraparantag

The investigational drug product is a sterile, isotonic, pH neutral solution for injection containing 6 mg/mL ciraparantag (10 mg/mL ciraparantag acetate) + 6.4 mg/mL sodium chloride to be administered by IV injection (See the Ciraparantag Investigator Brochure for complete description of the chemical structure).

#### 5.2.2 Placebo

Sterile 0.9% Sodium Chloride Injection, USP will be administered as the placebo in the same method as ciraparantag.

#### 5.2.3 Apixaban

All doses of apixaban (trade name Eliquis®; Pfizer/BMS) will be administered in an open-label manner. The ingestion of apixaban tablets will be witnessed by clinical site personnel.

Apixaban 10 mg administered twice daily Q12 as two 5 mg oral tablets for 3.5 consecutive days is a standard, FDA approved dose and is considered safe and well-tolerated in this population.

### **5.3 Selection and Timing of Dose for Each Volunteer Subject**

The doses of ciraparantag utilized in this study were selected based on the clinical findings in PER977-01-001.

The 10 mg dose for apixaban for 7 days is recommended for treatment of deep vein thrombosis and pulmonary embolism and is a FDA approved dose considered safe and well-tolerated in this population.

All doses of apixaban will be administered in an open-label manner. All doses of study drugs (ciraparantag or placebo) will be administered in a single-blind manner (study site personnel performing coagulation testing and subjects will be blinded).

### **5.4 Method of Assigning Patients to Treatment Groups**

The Investigator will identify all subjects who will meet all inclusion/exclusion criteria and who will be enrolled in the study. Subjects will be enrolled in cohorts of 16 subjects each and will be sequentially assigned Randomization Numbers 1001 to 1016 prior to dosing of study drug on Day 4, after confirmation of eligibility. The next 16 such subjects will be enrolled in Cohort 2, and will be sequentially assigned Randomization Numbers 2001 to 2016. This method of assignment will continue through all three cohorts. Replacement subjects, if applicable will be assigned the same treatment, using the number of the withdrawing subject +100 (e.g. if subject 1001 withdraws, the replacement subject would be 1101).

The assignment of treatment will be based on Randomization Schedules to be generated by the CRO. Each cohort will have a different, independently generated randomization schedule.

### **5.5 Blinding**

This is a single-blind study in which the subjects will be blinded to treatment of the study drug (ciraparantag or placebo) and the study personnel assigned to conducting coagulation testing (WBCT) must be blinded as well.

### **5.6 Concomitant Therapy**

Use of concomitant medications (including vitamin, nutritional and herbal supplements) is prohibited as per Exclusion criteria, during screening and for the course of the study. Acetaminophen up to 1 gram/24 hours may be administered for management of AEs at the discretion of the Investigator. As needed use of over-the-counter antihistamines is permitted following screening and prior to admission on Day -1 and following discharge from the clinical site on Day 4. Use of hormonal contraceptives is acceptable except for oral contraceptives.

## 5.7 Meals and Study Restrictions

### 5.7.1 Dietary Guidelines Prior to Check-in

The purpose of the required diet is to prevent a false positive reading for the fecal blood test.

Begin at least 2 days before check-in at the clinical site for overnight visits.

When to begin diet restriction?	Do not eat and drink	What are some suggested foods that are ok to eat and drink?
At least 2 days before check-in	Any red or rare meat. Horseradish, cantaloupe, raw turnips, broccoli, cauliflower, red radishes, and parsnips. NO alcohol (beer, wine or liquor)	Pasta, rice, potato, dairy, and vegetables Non-alcoholic beverages like sparkling cider, ginger-ale, Sprite, Crystal-light with no caffeine, whole milk (cow, goat, soy)

### 5.7.2 Dietary Guidelines during the Study

Meals and an evening snack will be provided for each overnight stay. Subjects will be instructed on when to fast, what times to eat meals and snacks, and when water may be consumed. Identical meals will be served for each treatment. The calorie content, as well as the percent of calories from protein, carbohydrate, and fat, will be uniform for each meal during the study (i.e., breakfast uniform to breakfast, lunch uniform to lunch). Substitutions of food are not allowed. The calories from fat for the day will not exceed 30% per day.

### 5.7.3 Lifestyle Restrictions

During the study, subjects will be advised against using manual razors and dental flosses. Electric razors and soft toothbrushes will be allowed.

Subjects will not perform any physical activity outside of their normal living activities and will not engage in strenuous activity from screening to study completion.

Except when ECGs must be taken in supine position, subjects will remain in the semi-erect or upright position with minimal ambulation (i.e. only to and from the washroom, lounge or for study procedures) for the first 8 hours after study drug dosing on Day 4.

## **5.8 Treatment Compliance**

All study drug will be administered by clinical site personnel by IV injection over a minimum of 10 minutes into an indwelling catheter that is not attached to an IV solution and will not result in dilution of the study drug. Following administration of the study drug, the indwelling catheter will be flushed with 5.0 mL of sterile 0.9% Sodium Chloride Injection, USP.

All doses of apixaban will be administered after meal with 240 ml of water under the supervision of clinical site personnel. The ingestion of all doses of apixaban will be witnessed by clinical site staff. A mouth and hand check of all subjects will be carried out to ensure that the tablets have been swallowed.

## **5.9 Dose Escalation/De-Escalation**

Review of WBCT results, AEs, clinical laboratory tests, and ECG data will be conducted by a group that includes the Principal Investigator, Medical Monitor(s), and representative(s) of the Sponsor. The group will be responsible for the decision to expand a given dose cohort, escalate (or de-escalate) to a different dose from the planned dose, or stop the study. All meetings will be documented with minutes.

The goal of the study is to explore the dose range of ciraparantag that reverses the anticoagulation induced by therapeutic doses of apixaban at steady state. The study is intended to establish a dose of ciraparantag that fully reverses steady-state apixaban, to evaluate at least one dose above the reversal dose to establish a therapeutic index, and at least one partial or no effect dose.

## **5.10 Packaging and Labeling**

### **5.10.1 Ciraparantag**

Ciraparantag Injection will be supplied as a sterile solution for IV injection containing 6 mg/ml ciraparantag (10 mg/mL ciraparantag acetate) and supplied in 30 clear vials (5 mL each). Vials will be labeled for clinical study use including study number, contents, quantity, lot number, date of manufacture and stability retest date, and storage conditions as well as a caution statement according to 21CFR 312.6(a).

### **5.10.2 Apixaban**

Apixaban will be provided in bottles containing 60 tablets per bottle (NDC 0003-0894-21). Bottles will be labeled for clinical study use including study number.

## **5.11 Storage and Accountability**

Drug supplies must be stored in a secure, limited access storage area under the recommended storage conditions.

### **5.11.1 Ciraparantag**

Ciraparantag will be stored refrigerated at 2-8°C (36-46°F) and shipped on cold packs to the clinical test site. Temperature will be monitored during shipping for excursions. After arrival at the clinical study site, it will be refrigerated at 2-8°C (36-46°F) until prior to administration.

### **5.11.2 Placebo**

Placebo solution will be provided by the CRO and stored at room temperature prior to preparation.

### **5.11.3 Apixaban**

Following the product Prescription Information, apixaban tablets must be stored at 20-25°C (68-77°F) with excursions permitted to 15-30°C (59-86°F). Temperature measurements will be recorded.

## **5.12 Investigational Product Retention at Study Site**

Investigational study drug will be labeled with the following statement – Caution: New Drug--Limited by Federal (or United States) law to investigational use. The Principal Investigator will maintain accurate records of receipt of all test articles, including dates of receipt. In addition, accurate records will be kept regarding when and how much of each test article is dispensed to and used by each individual subject in the study. Reasons for deviation from the expected dispensing regimen must also be recorded. A Drug Dispensing Form will be provided for this purpose and will be signed by the Principal Investigator at the conclusion of the study. To satisfy regulatory requirements regarding drug accountability and destruction, following instruction from the Sponsor, the Principal Investigator will arrange for return or destruction of all used, unused, empty and partially used study drug and containers to the Sponsor for final accountability and disposal.

## 6 STUDY PROCEDURES

### 6.1 Informed Consent

The Investigator or designee will obtain written informed consent from all subjects prior to initiation of any study-related procedures as per Section [10.5](#).

### 6.2 Medical History

The Investigator or designee will obtain a complete medical history including medication and surgical history will be obtained at the screening visit. To ensure subject safety, the Investigator may ask the subject to sign a medical release form allowing him to contact the subject's doctor for more information about subject's medical history

### 6.3 Physical Examination

The Investigator will perform a complete physical examination at screening and abbreviated physical examination will be performed on check-in and prior to discharge.

The full physical examination will consist of the following:

- General physical well-being will be assessed by evaluation of the head, eyes, ears, nose, throat, neck, heart, chest, lungs, abdomen, extremities, neurological status (including, but not limited to, consciousness, facial symmetry, strength/sensation symmetry, gait), skin, and other conditions of note
- Measurement of height in street clothes and without shoes (to the nearest 0.5 cm) at screening only
- Measurement of weight in street clothes and without shoes (to the nearest 0.1 kg). Weight will be assessed by standard objective means (e.g., weight scale). There are no adjustments in dose if changes in weight should occur
- Body mass index is based on height and weight calculated at screening and first check-in for eligibility purposes using the following formula:

$$\text{BMI} = \frac{\text{Weight in kilograms}}{\text{Height in meters}^2}$$

The abbreviated physical examination will consist of the following:

- General appearance, heart, lungs, abdomen.
- Additional physical examinations may be conducted at any time throughout the study, if deemed necessary by the Investigator.

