## STUDY PROCEDURES

Day→ Procedure ↓	Screening a	Treatment Period						Follow-up
	Day -36 to -1	Day -1 Check-in	Day 1	Day 2	Day 3	Day 4	Day 5	Day 7-10
Written informed consent	X							
Inclusion/exclusion criteria	X b	X						
Demographic data	X							
Height	X							
Weight	X	X						
Medical/ surgical history	X							
Medication history	X							
Physical exam c, d	X	X						X
Vital signs (BP and HR), RR and temp c, e	X	X	X	X	X	X	X	
Safety laboratories c, f	X	X						X
Fecal occult blood f		X						
Drug and alcohol screen g	X	X						
Viral hepatitis/HIV serology g	X							
12-lead ECG c, h	X	X	X	X	X	X	X	
Urine pregnancy test i	X							X
Serum Pregnancy test i		X						
Admission to CRU j		X						
Randomization							X	
Apixaban administration k			X	X	X	X		
Study drug administration k							X	
Stroke assessment k			X	X	X	X		
Experimental safety biomarker f			X				X	
PD measurements c, l			X			X	X	
PK sample collections m			X			X	X	
Adverse event monitoring	X	X	X	X	X	X	X	X
Concomitant medication	X	X	X	X	X	X	X	X
Discharge from clinical site								X
End of the study participation n								X

- Screening procedures are to be conducted -36 to -1 day before check-in on Day -1. All subjects will be provided lifestyle and dietary guidelines appropriate for an anticoagulant study and for fecal occult blood testing. If the screening visit takes place within 3 weeks prior to check-in, the check-in procedures may be modified to exclude redundant procedures at the discretion of the Investigator.
- Subjects should conform to the inclusion/exclusion criteria for the duration of the study. If a subject violates an inclusion or exclusion criterion at any point during the study, he/she may be removed from the study and replaced.
- When timing for assessments coincide, PD assessments will be performed first followed by PK assessment(s) and then safety assessments.
- A complete physical examination will be performed at screening. An abbreviated physical examination will be performed at check-in and prior to discharge from the clinical site.

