### 1.2.1 PER977-01-001

PER977-01-001 was a phase 1, first in human, double-blind, placebo-controlled, sequential group, two-period, ascending ciraparantag dose study administered alone and in combination with edoxaban in healthy volunteers. The study consisted of two periods: a single intravenous IV injection of 3 mg, 9 mg, 15 mg, 30 mg, 60 mg, 120 mg or 180 mg ciraparantag, respectively (ciraparantag acetate 5, mg, 15, mg, 25 mg, 50 mg, 100 mg, 200 mg, or 300 mg) alone or placebo with serial PK, pharmacodynamic (PD), and safety monitoring. After a one-week washout, a single dose of edoxaban 60 mg was administered followed 3 hours later by a single dose of ciraparantag or placebo at the same dosage as was administered in the first period, and with serial PK, PD, and safety monitoring.

The highest incidence of treatment emergent adverse events (TEAEs) in Period 1 (ciraparantag monotherapy) were in the system organ class (SOC) of general disorders and administration-site conditions (feeling hot; n=14, 24.1%), and in nervous system disorders (dysgeusia; n=8, 13.8%). Adverse events in placebo subjects comprised feeling cold, headache, infusion related reaction and peripheral coldness reported in one subject each.

The highest incidence of TEAEs in Period 2 was in the SOC of general disorders and administration-site conditions (feeling hot n=11, 17.2%), nervous system disorders (dysgeusia n=8, 12.5%), and in injury, poisonings, and procedural complications (contusion n=7, 10.9%). Adverse events in placebo subjects comprised feeling cold chest discomfort, infusion site coldness, vessel puncture site pain, dysgeusia, headache, contusion, infusion related reaction, peripheral coldness, and hematoma reported in one subject each.

No serious AEs were reported during the conduct of the study, no laboratory results were reported as AEs and there were no clinically significant changes in vital signs. There were no clinically significant AEs and no dose-related findings occurred with regard to interval prolongations in median of triplicate ECG tracings with regard to HR, P-R, QRS, QTcF or R-R intervals.

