## **9.11 Safety Endpoints**

Individual vital signs, ECG parameters, and clinical laboratory data will be listed and tabulated with descriptive statistics. For the laboratory safety data, out of range values will be tabulated in shift tables. Abnormal and clinically noteworthy ECGs will be tabulated.

Treatment-emergent AEs will be tabulated by MedDRA system organ class and preferred term, and further by severity and relatedness to study drug. SAEs and adverse events that lead to discontinuation will be listed.

Physical examination results will be listed. New onset abnormalities after dosing will be recorded as adverse events.

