4.8.6 Physical Examinations

A complete physical examination will be performed at screening visit, and an abbreviated physical examination will be performed on check-in and prior to discharge.

Physical examination results will be listed by subject and summarized by treatment.

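### The only scheduled physical examination after study drug leaves out skin, injection and puncture sites, limbs and neurological status, so its safety summary cannot speak to findings there

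*Protocol*

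**What the plan says.** Protocol 6.3 describes two examinations. The full one, done at screening only, includes "extremities, neurological status (including, but not limited to, consciousness, facial symmetry, strength/sensation symmetry, gait), skin, and other conditions of note". The abbreviated one consists of "General appearance, heart, lungs, abdomen". On timing, 6.3 says that the "abbreviated physical examination will be performed on check-in and prior to discharge", and footnote d of the Study Procedures table agrees: "An abbreviated physical examination will be performed at check-in and prior to discharge from the clinical site". Section 7.2.5 lists the abbreviated form for Day 5 or early termination, 6.12.1 lists it for withdrawals, and the Day 7-10 contact in 7.3 is a telephone call.

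The results are meant to be used. SAP 3.1.3 names physical examinations among the safety endpoints. SAP 4.8.6 states: "Physical examination results will be listed by subject and summarized by treatment". Protocol 9.11 adds: "New onset abnormalities after dosing will be recorded as adverse events".

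There are two supplementary routes. Section 6.3 allows that "Additional physical examinations may be conducted at any time throughout the study, if deemed necessary by the Investigator", without scheduling these examinations or setting their content. Section 6.5 provides a separate stroke assessment (face, arm, speech, gait, vision, headache) on Days 1 to 4, about 3 hours after the morning apixaban dose, with a window of 1 hour either side.

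**The concern.** Subjects take apixaban twice daily for three days and once on Day 4, and then receive an agent intended to restore clotting. Visible bleeding, changes at the injection and venipuncture sites, and limb swelling are natural things to look for afterwards. The one scheduled post-dose examination is not defined to look for them.

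The risk lies in interpretation. A by-treatment table with no new abnormalities may be read as evidence that there was no bruising or site reaction, when those areas need not have been examined in anyone. What is found then depends on what staff notice, what the subject volunteers, or whether the investigator orders a further examination. Protocol 5.3 and 5.5 require blinding only of subjects and of the staff who test coagulation. The investigator who makes that choice need not be blinded, so ascertainment could differ by arm.

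**Working it through.** The plan states no figure on this point. The check sets the provisions side by side and adds three short calculations.

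**1. Scope by visit**

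| Visit | Examination | Skin, limbs, neurological status |
|---|---|---|
| Screening (6.3, 7.1) | Full | Yes |
| Check-in, Day -1 (6.3, 7.2.1) | Abbreviated; may be omitted if screening was within 3 weeks | No |
| Day 4 after study drug (7.2.4) | None listed | No |
| Day 5 or early termination (7.2.5) | Abbreviated | No |
| Day 7-10 (7.3) | Telephone | No |

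No section schedules an inspection of skin, puncture sites or limbs after study drug. The last scheduled look at them is at screening, up to 36 days before check-in.

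**2. Apixaban doses before study drug** (3.1): 2 per day × 3 days + 1 = 7 doses of 10 mg.

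**3. Neurological cover from the stroke assessment**
- Window on Day 4 (6.5): 3 h ± 1 h, that is, 2 h to 4 h after apixaban.
- Study drug starts at about 3 h and runs for at least 10 minutes (3.1, 3.2), so it ends at 3 h 10 min at the earliest.
- Latest assessment relative to the end of injection: 4 h − 3 h 10 min = 50 min.
- The 24-hour point counts from the end of injection (section 7): 3 h 10 min + 24 h = 27 h 10 min after apixaban.
- Time with no scheduled structured neurological check: at least 27 h 10 min − 4 h = 23 h 10 min.
- Section 7.2.4.1 lists the Day 4 assessment among the procedures before study drug, so as written it gives no post-dose cover. The 50 minutes is the most its window allows. None is scheduled on Day 5.

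**4. What the earlier contusions show**
- Protocol 1.2.1, Period 2 (after single-dose edoxaban): 7 subjects, 10.9%.
- Implied denominator: 7 / 0.109 = 64.2, so about 64; check: 7 / 64 = 10.9%.
- Active subjects here: 16 × 3/4 = 12 per cohort, and 36 over three cohorts.
- If the same rate applied: 12 × 7/64 = 1.3 expected per active group and 36 × 7/64 = 3.9 over all active subjects. The chance of at least one among 12 is 1 − (57/64)^12 = 0.75.

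These figures describe how often contusion might occur. They do not estimate how many contusions would go unrecorded.

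**The case against.** The case on the other side has real weight.

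- **Adverse events need no examination to be captured.** Section 6.10 allows them to be directly observed, volunteered or found by general questioning. Subjects stay in the unit until 24 hours after study drug, and adverse events are recorded at 15, 30 and 45 minutes and 1, 3, 5 and 24 hours, each time with a blood draw. Staff will see venipuncture sites repeatedly, and general appearance may pick up gross signs. This stands, and it confines the point to scheduled, uniform ascertainment.
- **The stroke assessment exists.** A reader might infer that nothing scheduled looks for a focal deficit. The documents do not support that: 6.5 is a structured check and a separate safety endpoint. What remains is its timing, shown above.
- **Earlier reactions.** A reader might infer that the known reactions to ciraparantag would show on a fuller examination. Most would not. Feeling hot and dysgeusia are symptoms, feeling hot was transient in the heparin study (1.2.2), and flushing would be seen only while present. Section 1.2.1 lists the haematoma, puncture-site pain and infusion-site coldness among placebo subjects, one each. It also lists a placebo contusion and does not break the seven down by arm.
- **The 75% figure.** It is tempting to read it as the chance of missing a bruise. It is not. Section 1.2.1 does not say how its contusions were detected, and they may well have been found through ordinary adverse event capture.
- **Other monitoring.** WBCT runs to 24 hours and discharge laboratory tests are planned. These test blood, however, and do not inspect skin, sites or limbs.
- **No contradiction.** Protocol and SAP agree on the examination. This is a choice of scope, which keeps the severity low.

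**Conclusion.** The point holds in a limited form. After study drug, the only scheduled physical examination covers general appearance, heart, lungs and abdomen. A clean physical-examination summary therefore carries no systematic information on skin, injection and puncture sites or limbs. For neurological signs, the stroke assessment reaches at most about 50 minutes past a 10-minute injection.

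The size of any under-recording cannot be estimated from the documents. The earlier contusions show only that such events occur in anticoagulated volunteers. Carrying their rate over would assume that single-dose edoxaban resembles repeated apixaban, and the denominator of 64 is itself inferred. The conclusion does not depend on that rate. It rests on the definition in 6.3 and on the absence of any other scheduled inspection. Severity is minor: a cheap improvement to the safety data, with no bearing on the primary WBCT analysis.

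**What to change.** In Protocol 6.3, extend the abbreviated examination to include skin (with injection and venipuncture sites), extremities, and the brief neurological items already listed for the full examination. Apply this at check-in and at Day 5 or early termination, so that a new-onset finding is judged against a baseline of the same scope. Where the check-in examination is omitted under 7.2.1, state that the full screening examination is the comparator; by that rule it is no more than 3 weeks before check-in. SAP 4.8.6 can then summarise these body systems by treatment.

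The cost is a few extra minutes at examinations already scheduled and a small case report form edit, with no added visit, sample or staff. The change makes the scope uniform across subjects. It does not blind the examiner, so that limitation would remain.
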